### 8.1.3 Supplementary Analyses

A mixed-effects model for repeated measures (MMRM) analysis will be used to estimate the mean change from baseline in the monthly number of headache days of at least moderate severity for the overall 3-month treatment period and by each month to support the primary analysis.

The MMRM will include treatment, sex, country, baseline preventive migraine medication use, month and treatment-by-month interaction as fixed effects and baseline value and years since onset of migraines as covariates. The unstructured covariance structure will be used for repeated observations within a subject. Kenward-Roger approximation will be used to estimate denominator degrees of freedom. The LS means for the treatment groups, LS means for the treatment differences (each TEV-48125 group – placebo group), and corresponding 95% confidence intervals and associated p-values will be calculated by month and for the overall treatment period.

The following SAS code pertains to the MMRM analysis.

```
proc mixed method = reml;
  class USUBJID MONTH TREATMENT SEX PRVMBASE CONTRY;
  model CHG = BASE TTMIG PRVMBASE SEX TREATMENT MONTH
    TREATMENT * MONTH CONTRY /s ddfm = kr;
  repeated MONTH /subject = USUBJID type = un r;
  lsmeans TREATMENT TREATMENT * MONTH / pdiff cl alpha = 0.05;
  ods output diffs = DIFFS lsmeans = LSMEANS;
run;
*PRVMBASE: Baseline preventive medication use
*TTMIG      : Years since onset of migraines
```

If any problems in convergence status arise in the estimation of variance components, heterogeneous Toeplitz, heterogeneous autoregressive of order 1, and heterogeneous compound symmetry, which are error variance-covariance structures, will be applied in that order, and the first structure that achieves convergence will be used. If anything other than an unstructured variance-covariance structure is selected, a sandwich estimator for standard errors will be used.

The LS means  $\pm$  SE of monthly change from baseline values estimated by MMRM will be plotted by month for each treatment group.

Mean change from baseline in the monthly number of headache days of at least moderate severity during the 4-week period after each dose (ie, for Month 1, Month 2, and Month 3) will also be estimated and compared by the same ANCOVA model as described in [Section 8.1.1](#) and by Wilcoxon rank-sum test as described in [Section 8.1.2](#).

#### 8.1.4 Technical Computational Details for Primary Analysis

- Definition of headache day of at least moderate severity  
A headache day of at least moderate severity is defined as when at least one of the following situations occurs:
  - A calendar day (0000 to 2359) with headache pain that lasts  $\geq 4$  hours with a peak severity of at least moderate severity
  - A calendar day (0000 to 2359) when the subject used acute migraine-specific medication (triptans or ergots) to treat a headache of any severity or duration
- Variable definitions

The change from baseline in the monthly average number of headache days of at least moderate severity during the 12-week period after the first dose of IMP will be derived using the electronic headache diary data collected for the corresponding headache diary questions. The baseline value will be calculated using all data collected from the day of V1/Screening through the day before V2/Baseline and normalized to 28 days (ie, if the number of days from V1/Screening through the day before V2/Baseline is greater or less than 28 days, the baseline value will be normalized to 28 days; see the following formula).

$$\frac{\sum \text{Days of efficacy variable during the screening period}}{\sum \text{Days with assessments recorded in the eDiary for the screening period}} \times 28$$

The monthly average number of headache days of at least moderate severity during the 12-week period after the first dose of IMP will be derived and normalized to 28 days (see the following formula), if a subject has  $\geq 10$  days of electronic headache diary data after the first dose of IMP.

$$\frac{\sum \text{Days of efficacy variable over the 12 week period}}{\sum \text{Days with assessments recorded in the eDiary for the 12 week period}} \times 28$$

The monthly number of headache days of at least moderate severity during the 4-week period after each dose (ie, for Month 1, Month 2, and Month 3), will be

derived and normalized to 28 days (see the following formula), where monthly data separated by each visit for IMP dosing will be used. If a subject is withdrawn early or has intermittent missing days and has <10 days of electronic headache diary entries for a month, that month's value will be considered as missing.

$$\frac{\sum \text{Days of efficacy variable during the 4 week period}}{\sum \text{Days with assessments recorded in the eDiary for the 4 week period}} \times 28$$

## 8.2 Secondary Endpoint

### 8.2.1 Secondary Analysis

The secondary endpoints in this trial are as follows:

- 1) Mean change from baseline in the monthly average number of migraine days during the 12-week period after the first dose of IMP
- 2) Proportion of subjects reaching at least 50% reduction in the monthly average number of headache days of at least moderate severity during the 12-week period after the first dose of IMP
- 3) Mean change from baseline in the monthly average number of days with use of any acute headache medications during the 12-week period after the first dose of IMP
- 4) Mean change from baseline in the monthly average number of headache days of at least moderate severity during the 12-week period after the first dose of IMP in subjects not receiving concomitant preventive migraine medications
- 5) Mean change from baseline in disability score, as measured by the HIT-6, at 4 weeks after the final (third) dose of IMP

For the endpoint 1), 3) and 4), will be analyzed using an ANCOVA model, Wilcoxon rank-sum test, and MMRM in the same manner as described in [Section 8.1](#). The LS means  $\pm$  SE of monthly change from baseline values estimated by the MMRM will also be plotted.

For the endpoint 2), each TEV-48125 group and the placebo group will be compared using Cochran-Mantel-Haenszel (CMH) test stratified by baseline preventive medication use. The difference in the endpoint 2) between each TEV-48125 group and the placebo group and its two-sided 95% confidence interval (a Mantel-Haenszel estimator of the difference and its two-sided 95% confidence interval) will be computed. Additionally, two-sided 95% confidence interval for the endpoint 2) in each treatment group will also be calculated using Clopper-Pearson method. Furthermore, proportion of subjects reaching at least 50% reduction in the monthly number of headache days of at least moderate severity during the 4-week period after each dose (ie, for Month 1, Month 2,

and Month 3) will also be computed in the same manner. Missing data of evaluation will not be imputed.

For the endpoint 5), the HIT-6 total score will be used for disability score. The ANCOVA model and Wilcoxon rank-sum test will be performed as described in [Section 8.1](#).

Frequency distributions will be provided by grade in each time point for each item of HIT-6.

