## **4 Sample Size**

In a phase 2b trial in CM patients (Trial LBR-101-021), concerning the mean change from baseline in the monthly average number of headache days of at least moderate severity during the 12-week period after the first dose of IMP, the difference between the TEV-48125 675/225/225 mg group and the placebo group was 1.7 days and the standard deviation was 4.9 days. On the assumption that this trial will also yield a similar result to the phase 2b trial (Trial LBR-101-021), a sample size of 176 subjects per group gives more than 90% power for the trial to succeed at a significance level of 0.05 (two-sided). Based on the above and taking into account a small percentage of subjects who may be excluded from the FAS, the target sample size was determined to be 180 subjects per group and 540 subjects as the overall total included in the trial.

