### **8.1 Primary Endpoint**

#### **8.1.1 Primary Analysis**

The primary efficacy endpoint is mean change from baseline in the monthly average number of headache days of at least moderate severity during the 12-week period after the first dose of IMP.

The primary endpoint will be analyzed using an analysis of covariance (ANCOVA) model. The model will include treatment, sex, country, and baseline preventive medication use as fixed effects and baseline number of headache days of at least moderate severity and years since onset of migraines as covariates. Two-sided 95% confidence intervals and p-values will be constructed for the least squares (LS) mean differences between each TEV-48125 group and the placebo group.

The following sample SAS code pertains to the primary analysis.

```
proc mixed;  
  class TREATMENT SEX PRVMBASE CONTRY;  
  model CHG = BASE TTMIG PRVMBASE SEX TREATMENT CONTRY /s;
```

```
lsmeans TREATMENT /pdiff cl alpha = 0.05;
ods output diffs = DIFFS lsmeans = LSMEANS;
run;
*PRVMBASE: Baseline preventive medication use
*TTMIG      : Years since onset of migraines
```

Multiplicity problems will be avoided using a closed testing procedure. If superiority of the TEV-48125 675/225/225 mg group to the placebo group is confirmed at a two-sided significance level of 0.05, then the TEV-48125 675 mg/placebo/placebo group vs the placebo group will be tested at a two-sided significance level of 0.05.

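### The CMH test for the 50% responder endpoint is valid but adjusts only for preventive use; adding the primary model's other covariates could bring a small, optional gain in precision

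*SAP*

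**What the plan says.** Secondary endpoint 2) is defined in SAP Section 8.2.1 as "Proportion of subjects reaching at least 50% reduction in the monthly average number of headache days of at least moderate severity" over the 12 weeks after the first dose. Under that section, each active group and placebo "will be compared using Cochran-Mantel-Haenszel (CMH) test stratified by baseline preventive medication use", with no other stratification factor, and the section also reports "a Mantel-Haenszel estimator of the difference and its two-sided 95% confidence interval". The effect scale is therefore a risk difference.

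Section 8.1.1 analyses the change in the same diary variable, over the same period and in the same analysis set, by ANCOVA: "The model will include treatment, sex, country, and baseline preventive medication use as fixed effects and baseline number of headache days", together with "years since onset of migraines as covariates". The MMRM in Section 8.1.3 uses the same covariates. Secondary endpoints 1), 3), 4) and 5) are referred back to Section 8.1. Endpoint 2) is the only secondary endpoint analysed without these terms.

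The one-factor CMH is also used for the responder endpoints in Sections 8.3.1 and 8.3.2 and for PGIC in Section 8.3.4, so the plan treats its binary endpoints consistently.

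**The concern.** Each subject's own baseline is the denominator of the percent reduction, so baseline headache days may predict who reaches 50%. The FAS definition in Section 5.1 requires baseline diary data, so this covariate exists for every analysed subject at no extra cost. If it does predict response, leaving it out gives a somewhat wider interval and lower power than the data allow. A chance baseline imbalance between arms would also be adjusted for in the primary result but not in its responder counterpart.

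What is at stake is efficiency on one secondary endpoint. The validity of the test is not in question.

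**Working it through.** **1. The plan's own figure.** Section 4 states that "the difference between the TEV-48125 675/225/225 mg group and the placebo group was 1.7 days", that "the standard deviation was 4.9 days", and that "a sample size of 176 subjects per group gives more than 90% power" at two-sided 0.05.

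- Standard error = 4.9 × √(2/176) = 0.522
- z = 1.7/0.522 = 3.25
- Power = Φ(3.25 − 1.96) = 90.2%

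The figure reproduces. It concerns the primary endpoint only. No responder rate, power or sample size is given for endpoint 2).

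**2. Simulation built from the primary assumptions.** From Section 4: 180 per arm, effect 1.7 days, SD 4.9 days. Assumed, because the SAP gives none of these: baseline mean 13, SD 5.5, truncated to 4 to 28; placebo mean change -3; slope of change on baseline from 0 to -0.5. The comparison is CMH by preventive use against the standardized risk difference from a logistic model. Run A used 2000 trials per setting. Run B also held post-baseline counts within 0 to 28. The variance ratio is adjusted over unadjusted.

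| Slope | Run A power, CMH → adjusted | Run A variance ratio | Run B power, CMH → adjusted |
|---|---|---|---|
| 0 | 61.3% → 67.2% | 0.89 | 58% → 63% |
| -0.1 | 62.1% → 65.9% | 0.93 | – |
| -0.2 | 66.8% → 69.7% | 0.96 | 67% → 69% |
| -0.3 | 71.9% → 72.5% | 0.98 | 72% → 73% |
| -0.4 | 75.4% → 75.5% | 1.00 | no gain |
| -0.5 | 80.7% → 81.1% | 1.01 | no gain |

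Run B also showed no gain when change was proportional to baseline. Under the null (slope -0.1 in run A), rejection was 4.6% for CMH and 4.7% adjusted; in run B it was about 5% for both.

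**3. Do the variance ratios and power gains agree?** Adjusted power = Φ[(1.96 + Φ⁻¹(power))/√ratio − 1.96].

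- Slope 0, from 58%: (1.96 + 0.20)/√0.89 = 2.29, and Φ(2.29 − 1.96) = 63%.
- Slope -0.2, from 67%: (1.96 + 0.44)/√0.96 = 2.45, and Φ(2.45 − 1.96) = 69%.
- Slope -0.3, from 72%: (1.96 + 0.58)/√0.98 = 2.57, and Φ(2.57 − 1.96) = 73%.

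An 11% variance reduction is thus worth about 5 points. Run A's 5.9 points at slope 0 is slightly higher; the Monte Carlo standard error of one such power is √(0.61 × 0.39/2000) = 1.1 points.

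**4. A check by prognostic strength.** Let R² be the share of responder variance that the omitted covariates explain. The effective size per arm is 176/(1 − R²). Responder rates of 15% and 28% are assumed.

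| R² | Effective n per arm | Power |
|---|---|---|
| 0 | 176 | 84.6% |
| 1% | 176/0.99 = 178 | 85.0% |
| 5% | 176/0.95 = 185 | 86.4% |
| 10% | 176/0.90 = 196 | 88.2% |

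With assumed baseline means of 12 to 15 and SDs of 4 to 6, baseline headache days explained 0% to 15% of responder variance for baseline-change correlations from -0.5 to 0. For correlations of -0.3 to -0.5 they explained only 0% to about 5%.

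**5. Finer CMH strata instead of a model.** With 16 strata (preventive use × country × sex × baseline split) and assumed rates of 20% and 32%, power fell from 74.0% to 71.7% when the covariates had no prognostic value, and from 73.1% to 71.6% when they were weak.

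**The case against.** The strongest reply is that nothing here is wrong. A prespecified CMH test with a Mantel-Haenszel risk difference is valid, the plan uses it for its other responder endpoints too, and a binary endpoint need not carry the ANCOVA covariates. That stands.

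The gain also depends on inputs absent from the SAP, and it is largest at slope 0, where baseline does not predict change at all. That setting is hard to believe for a bounded count, and it produces negative post-baseline values in subjects with low baselines. Holding the counts within 0 to 28 does not remove the gain, because a value raised to zero is still a response. But the implausibility of slope 0 stands, so the upper end of the range is unlikely. Because percent reduction already divides by baseline, roughly proportional improvement leaves little for baseline to explain. The argument from chance imbalance weakens to the same degree.

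The stakes are low. The closed testing in Section 8.1.1 orders only the two dose comparisons of the primary endpoint, and the SAP attaches no power target or controlled alpha to endpoint 2).

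Two replies do not hold against the proposed analysis. It does not replace the planned effect measure with a conditional odds ratio, because the standardized risk difference is marginal and stays on the scale that Section 8.2.1 already reports. The loss seen with 16 strata does not apply either, because the model needs no such strata.

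**Conclusion.** This is an optional efficiency improvement, not an error. Adjusting endpoint 2) for the remaining 8.1.1 covariates may add about 0 to 5 power points and lower the variance by 0% to 11%. This rests on the assumed baseline (mean 13, SD 5.5), the assumed placebo change (-3) and the range of slopes tried. The gain is nil if change is roughly proportional to baseline. No setting showed a material loss from model-based adjustment, and type I error stays near 5%.

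A reader might infer more, and the SAP does not support it:

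- **That the planned test certainly loses power, or is invalid.** The SAP states neither responder rates nor how strongly baseline predicts response, and several plausible settings show no gain.
- **That the CMH omits randomization strata.** The SAP does not name the randomization stratification factors, so it gives no basis for this argument.
- **That country should be added as a CMH stratum, or that PGIC should change too.** Neither was shown to help, and PGIC has no baseline denominator.

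**What to change.** Before unblinding, specify in Section 8.2.1 for endpoint 2) a logistic regression with the 8.1.1 terms (treatment, sex, country, preventive use, baseline headache days, years since onset). Report the standardized (marginal) risk difference for each active group versus placebo with a robust 95% CI and p-value. Keep the CMH test and the Mantel-Haenszel difference as supportive results.

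Sections 8.3.1, 8.3.2 and 8.3.4 borrow their method from endpoint 2), directly or through one another. The new wording should therefore say which analyses stay on CMH: the 100% threshold, where few responders could make the model unstable, and PGIC.

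The cost is a paragraph of SAP text and a short program, with no new data. If the sponsor prefers the CMH as the main analysis, a sentence giving the reason would be enough.

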### **8.2.2 Technical Computational Details for Secondary Analysis**

- Definition of migraine day

A migraine day is defined as when at least one of the following situations occurs:

- A calendar day (0000 to 2359) demonstrating at least 4 consecutive hours of headache meeting the criteria for migraine with or without aura
- A calendar day (0000 to 2359) demonstrating at least 4 consecutive hours of headache meeting the criteria for probable migraine, a migraine subtype where only one migraine criterion is missing
- A calendar day (0000 to 2359) with headache of any duration that was treated with migraine specific-medication (triptans and ergot compounds)

The derivation logic is presented in [Appendix 1](#).

- Variable definitions

- Electronic Headache Diary Data

The monthly average number of days for secondary endpoints (eg, migraine days, days with use of any acute headache medications, etc.) during the 12-week period after the first dose of IMP will be derived similar to the primary endpoint using the electronic headache diary data collected for the corresponding headache diary questions. The baseline value and monthly number of days for endpoints during the 4-week period after each dose (ie, for Month 1, Month 2, and Month 3) will be derived in the same manner (see [Technical Computational Details for Primary Analysis 8.1.4](#)).

- 6-Item Headache Impact Test (HIT-6)

The HIT-6 total score will be obtained from summation of the 6 question points. Each question is answered on the scale ranging with the following response options: 6 points (never), 8 points (rarely), 10 points (sometimes), 11 points (very often), and 13 points (always). If one or more items are missing, then the total score is missing. Baseline will be the last value prior to the first dose of IMP. Post-baseline (4 weeks after the final [third] dose of IMP) will be the nominal visit.

## **8.3 Exploratory Endpoints**

### **8.3.1 Number of Headache Days of at Least Moderate Severity**

The exploratory endpoints for number of headache days of at least moderate severity in this trial are as follows:

- 1) Mean change from baseline in the weekly number of headache days of at least moderate severity during the 4-week period after the first dose of IMP
- 2) Proportion of subjects reaching at least 75% reduction and total (100%) reduction in the monthly average number of headache days of at least moderate severity during the 12-week period after the first dose of IMP
- 3) Proportion of subjects reaching at least 50% reduction and at least 75% reduction in the number of headache days of at least moderate severity during the 4-week period after the first dose of IMP for whom this level of effect is sustained throughout the 12-week period after the first dose of IMP
- 4) Mean change from baseline in the monthly average number of headache days of at least moderate severity during the 12-week period after the first dose of IMP in subjects receiving concomitant preventive migraine medications
- 5) Mean change from baseline in the number of headache days of at least moderate severity during the 4-week period after the first dose of IMP

For the endpoint 1), similar to the supplementary analysis for the primary endpoint described in [Section 8.1.3](#), an ANCOVA model, Wilcoxon rank-sum test, and MMRM will be used to estimate the mean change from baseline by week (ie, for Week 1, Week 2, Week 3 and Week 4) after the first dose of IMP.

The endpoint 2) will be analyzed using CMH method as described in [Section 8.2.1](#) “endpoint 2)”.

The endpoint 3) will be analyzed using CMH test stratified by baseline preventive migraine medication use similar to “endpoint 2)” in [Section 8.2.1](#). If the subject shows 50% reduction or more at Month 1, Month 2, and also Month3, the level of effect is considered to be sustained throughout the 12-week period after the first dose of IMP for this subject. A subjects with a missing will be treated as a non-responder. Similar definition will be applied to calculate the proportion of sustained responders reaching at least 75% reduction.

The endpoint 4) will be analyzed using an ANCOVA model, Wilcoxon rank-sum test, and MMRM in the same manner as described in [Section 8.1](#).

The endpoint 5) will be compared between the combined TEV-48125 group and the placebo group, since the patients randomized to both active treatment arms receive the

same dose of TEV-48125 675 mg at first dose of IMP. Similar analyses described in [Section 8.1](#) will be used. An MMRM will be used to estimate the mean change from baseline by week (ie, for Week 1, Week 2, Week 3 and Week 4) after the first dose of IMP, and an ANCOVA model and Wilcoxon rank-sum test will be used to estimate the mean change from baseline for Month 1 after the first dose of IMP.

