### **8.3.2 Number of Migraine Days**

The exploratory endpoints for number of migraine days in this trial are as follows:

- 1) Mean change from baseline in the weekly number of migraine days during the 4-week period after the first dose of IMP
- 2) Proportion of subjects reaching at least 50% reduction, at least 75% reduction, and total (100%) reduction in the monthly average number of migraine days during the 12-week period after the first dose of IMP
- 3) Proportion of subjects reaching at least 50% reduction and at least 75% reduction in the number of migraine days during the 4-week period after the first dose of IMP for whom this level of effect is sustained throughout the 12-week period after the first dose of IMP
- 4) Mean change from baseline in the monthly average number of migraine days during the 12-week period after the first dose of IMP in subjects not receiving concomitant preventive migraine medications
- 5) Mean change from baseline in the monthly average number of migraine days during the 12-week period after the first dose of IMP in subjects receiving concomitant preventive migraine medications
- 6) Mean change from baseline in the number of migraine days during the 4-week period after the first dose of IMP

The endpoint 1) will be analyzed in the same manner as “endpoint 1)” in [Section 8.3.1](#).

The endpoint 2) will be analyzed in the same manner as “endpoint 2)” in [Section 8.3.1](#).

The endpoint 3) will be analyzed in the same manner as “endpoint 3)” in [Section 8.3.1](#).

The endpoints 4) and 5) will be analyzed in the same manner as “endpoint 4)” in [Section 8.3.1](#).

The endpoint 6) will be analyzed in the same manner as “endpoint 5)” in [Section 8.3.1](#).

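### The 100% reduction endpoints inherit a Mantel-Haenszel difference interval with no sparse-data rule: it is 0 to 0 with no events, and too short when a few active subjects and almost no placebo subjects respond

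*SAP*

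**What the plan says.** Section 8.3.1, endpoint 2), includes "total (100%) reduction in the monthly average number of headache days of at least moderate severity during the 12-week period". Its analysis is fixed by one sentence, "The endpoint 2) will be analyzed using CMH method as described in" Section 8.2.1, endpoint 2). Section 8.3.2, endpoint 2), includes "total (100%) reduction in the monthly average number of migraine days during the 12-week period" and refers back to Section 8.3.1.

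Section 8.2.1, written for the 50% responder endpoint, supplies three elements:
- a test: each active group and placebo are "compared using Cochran-Mantel-Haenszel (CMH) test stratified by baseline preventive medication use";
- a between-group interval: "a Mantel-Haenszel estimator of the difference and its two-sided 95% confidence interval";
- an exact interval per arm: a 95% interval "in each treatment group will also be calculated using Clopper-Pearson method".

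The SAP does not name the variance or the type of limit for the Mantel-Haenszel interval, states no rule for sparse or zero events, and gives no expected rate of complete response. The results go into tables CT-6.2.2.2 (headache days) and CT-6.3.2.3 (migraine days) of Appendix 5.

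**The concern.** A complete responder has no qualifying day in any diary entry over 12 weeks. The trial enrols chronic migraine patients, and under Section 8.1.4 a day also counts when a triptan or ergot is taken for a headache of any severity or duration. Few such subjects is a reasonable expectation, although the SAP does not state it.

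An interval of the form estimate ± 1.96 × SE takes its SE from the observed counts. With no events the SE is zero, and with one or two events it is small. A difference table for complete response could then show no uncertainty at all, or too little on the upper side. With no events the CMH statistic is 0/0, and the SAP does not say what is printed in its place.

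**Working it through.** **Inputs.** 180 per group, allocated 1:1:1 (SAP Sections 4 and 3.1). Two strata, baseline preventive medication yes or no. Section 3.3.1 caps users at 30% of the sample, so at the cap each arm splits 54/126 (assumption: cap reached, same rate in both strata). A separate simulation with strata 20/80 gave the same coverage to rounding. All event rates are assumptions.

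**The plan's own figure.** There is none for these endpoints. The Section 4 power claim concerns the primary endpoint and matters here only as the source of the arm size. It reproduces: 1.7 / (4.9 × √(2/176)) = 3.25, and Φ(3.25 − 1.96) is about 90.2%, against a stated value above 90%.

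**Formula.** With x1, x0 events among n1, n0 subjects in a stratum, N = n1 + n0 and W = Σ n1n0/N:
- estimate d = Σ[(x1n0 − x0n1)/N] / W;
- Greenland-Robins variance = Σ{[x1(n1 − x1)n0³ + x0(n0 − x0)n1³] / (n1n0N²)} / W².

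With equal arms of m per stratum, W = 27 + 63 = 90, d = (total x1 − total x0)/180, and the variance is Σ{[x1(m − x1) + x0(m − x0)]/(4m)} / 8100. The Sato variance gave the same intervals to two decimals in every case below.

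**Observed counts (percentage points).**
- 0 versus 0: every term is zero, so the interval is 0 to 0. Newcombe gives −2.09 to +2.09 and Miettinen-Nurminen −2.10 to +2.10.
- 1 versus 0 (event in the stratum of 126): variance = [125/504]/8100, SE = 0.553 points, interval 0.56 ± 1.08 = −0.53 to 1.64. Miettinen-Nurminen: −1.55 to 3.09.
- 3 versus 0 (1 and 2 by stratum): variance = [53/216 + 248/504]/8100, SE = 0.954 points, interval 1.67 ± 1.87 = −0.20 to 3.54. Miettinen-Nurminen: −0.45 to 4.79.

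**Coverage of the nominal 95% interval.** Mantel-Haenszel and Newcombe by full enumeration of the binomial outcomes. Newcombe and Miettinen-Nurminen are unstratified at 180 per arm; a dash means not computed.

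| True rate, active vs placebo | P(no events) | Mantel-Haenszel | Newcombe | Miettinen-Nurminen |
|---|---|---|---|---|
| 0.5% vs 0% | 40.6% | 59.4% | 100% | 99.8% |
| 1% vs 0% | 16.4% | 83.4% | 99.8% | 99.0% |
| 1% vs 0.5% | 6.6% | 89.1% | 99.4% | 97.5% |
| 1.5% vs 0% | 6.6% | 93.2% | 99.8% | – |
| 2% vs 0% | 2.6% | 87.3% | 99.6% | 97.1% |
| 3% vs 0% | 0.4% | 90.0% | 98.7% | 95.0% |
| 2% vs 0.5% | 1.1% | 94.6% | 98.8% | – |
| 3% vs 1% | 0.1% | 94.0% | 97.6% | 94.6% |
| 0.5% both | 16.5% | 98.9% | 99.8% | – |
| 1% both | 2.7% | 96.3% | 98.7% | – |
| 2% both | 0.1% | 95.5% | 96.6% | – |

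The low values can be traced by hand. At 0.5% versus 0%, P(no events) = 0.995^180 = 40.6%. The interval 0 to 0 then misses the true 0.5 points, and 100 − 40.6 = 59.4%. At 2% versus 0%, the interval misses with no events (2.6%) and also with one event, whose upper limit is at most about 1.64 points: 180 × 0.02 × 0.98^179 = 9.7%. Together that is 12.3% of the 12.7% shortfall from 100%. At 1.5% versus 0% the one-event interval reaches the truth, so coverage rises to 93.2%.

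**The test.** Exact size of the stratified CMH test at a nominal 5% with equal rates, counting no events as non-rejection: 1.1% at 0.5%, 3.7% at 1%, 4.5% at 2%. Unstratified Fisher: 0.03%, 0.4% and 1.5%.

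**The case against.** The other side has a good deal in its favour.

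- **General undercoverage.** A reader might infer that the interval covers well below 95% whenever complete responders are few. It does not. At equal rates from 0.1% to 3% coverage runs from 100% down to 95.3%, because even 0 to 0 contains a true difference of zero. The shortfall needs unequal rates with placebo at or near zero.
- **Collapse.** A reader might extend this to any small count. Only zero events in both arms gives 0 to 0; with one or three events the interval is short but has width.
- **Misleading p-values.** For 4/180 versus 0/180 the CMH p-value is 0.045 and Fisher's is 0.12, which might suggest that the planned test is unsafe. The sizes above show otherwise: CMH stays below 5% in every setting tried, and the gap reflects Fisher's conservatism. An exact test is not needed for validity and would cost power.
- **A specified Wald interval.** The SAP names only the estimator and a 95% interval. That the limits are estimate ± 1.96 × SE is an inference from usual practice.
- **Existing safeguard.** The per-arm Clopper-Pearson interval comes with the same cross-reference and stays valid: 0/180 gives 0 to 2.03%. It shows uncertainty beside the difference, but it is not an interval for the difference.
- **Rarity and rank.** Rarity is assumed, and both endpoints are exploratory and outside the closed testing procedure of Section 8.1.1.

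These points narrow the concern. They do not remove the 0 to 0 interval, the undefined statistic, or the low coverage when the drug produces a few complete responders and placebo almost none.

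**Conclusion.** The point holds in a limited form. Sections 8.3.1 and 8.3.2 reuse the Section 8.2.1 difference interval for complete response without naming the limit method or saying what happens when events are sparse or absent. Under the usual variances this fails outright with no events. It covers roughly 59% to 90% in most of the settings tried with placebo at or near zero and a higher active rate, and is close to or above nominal elsewhere. The size rests on assumed rates, 180 per arm, equal rates across strata and the usual variance. It does not extend to the CMH test, the per-arm intervals or the 50% analysis. It is a cheap improvement to two exploratory tables and changes no confirmatory conclusion.

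**What to change.** Add to Section 8.3.1, endpoint 2), with Section 8.3.2 following by its existing cross-reference: for the 100% reduction tables (CT-6.2.2.2 and CT-6.3.2.3), the 95% interval for the between-group difference is computed by a stratified score method (Miettinen-Nurminen type) or a stratified Newcombe method, with the choice fixed in advance; when no subject in either compared arm has an event, no CMH p-value is reported. Keep the stratified CMH test and the per-arm Clopper-Pearson intervals, and leave the 50% analysis as it is.

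The cost is a sentence or two and a different confidence-limit option. Intervals become somewhat wider: at 3 versus 0 events the width goes from 3.74 points (−0.20 to 3.54) to 5.24 (−0.45 to 4.79). The comparison figures here are unstratified, so the stratified versions will differ slightly.
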